Height will be measured at the screening visit and the baseline visit using a portable stadiometer. The patient will be asked to remove their shoes and have their heels, buttocks and upper part of the back remain in contact with the stadiometer with their arms hanging naturally at their side. The patient is asked to inhale and hold their breath, while the technician lightly applies traction to the patient's head in order to maintain alignment with the Frankfort Plane. The slide is lowered until it reaches the vertex of the skull and the reading from the indicator is recorded to the nearest 0.1 centimeter. This process will be repeated, and if the two readings differ by more than 0.5 cm, a third measurement will be obtained. The closest two measurements will be averaged for analysis. Calibration of the portable stadiometer is not required, however the accuracy of the stadiometer will be checked at scheduled monitoring visits against a standard meter stick. It is not necessary for the stadiometer to be calibrated once all Baseline Visits are completed as height is not measured at follow-up measurement visits.

Questionnaires

All questionnaires will be interviewer administered and data-entered by research staff. Paper questionnaires will be used in the event of power or other equipment failure.

Baseline Demographic and Health History Questionnaire

A self-report demographic and health history questionnaire asks the patients about their age, sex, race/ethnicity, use of tobacco and alcohol, health insurance status, income and employment, education level, history of chronic diseases, and cellular phone ownership and internet use.

Change in Health History Questionnaire

A self-report questionnaire captures changes in health outcomes that have occurred across the 6 months of the intervention. This questionnaire is administered at the 6 and 12 assessment visits.

Patient-reported Quality of Life

PROMIS: Global Health, Physical Health, Mental Health, Physical Function, Social Isolation

PROMIS® stands for the Patient Reported Outcomes Measurement Information System

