Follow-up Assessments. For follow-up assessments at month 6 and month 12, a trained staff will conduct measures of a point of care HbA1c, weight and surveys/questionnaires completed by participants. Patient-reported surveys/questionnaires may be completed in-person or over the phone prior to the in-person visit depending on participant preferences. For all in-person visits, telephone calls will be made to schedule these visits and provide reminders for upcoming visits. Reminder calls will occur 1-7 days prior to scheduled appointments.

Chart Review: Medical Record Data Collection

In addition to data collection of outcome measurements by the research staff, a chart review data collection effort will be done by utilizing the medical records at the participating clinics. For each of the participating patients in both arms, a retrospective chart review covering the period of the intervention will be done to abstract data on clinical variables of interest over the course of the intervention. The electronic medical records of the patients will be obtained, or in cases where electronic records are not available, paper medical records will be abstracted by hand and data-entered by research staff.

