- d) Increased physical activity. Patients in the intervention arm will be counseled to increase physical activity to levels that are consistent with the recommendations for US adults (30 minutes of moderate intensity activity per day). There is the possibility of adverse events such as minor musculoskeletal problems, but risk is minimized by excluding potential participants with contraindications to exercise. Considering these types of events are expected in this trial they will not be recorded or reported unless they meet the definition of a Serious Adverse Event. Patients are counseled to secure physician approval before beginning any new exercise plan.
- e) Gastrointestinal (GI) upset from taking metformin. For patients enrolled in the lifestyle plus metformin recommendations, we will ask patients to monitor their symptoms. Metformin is recommended by the American Diabetes Association for the prevention of diabetes among those at high-risk. To minimize nausea and GI upset, in the Orientation for providers and provider handout on metformin therapy recommendations, materials will describe how to start patients at low dose of 250mg daily and increase to 250mg twice daily after 2 weeks as tolerated. Enrolled participants who do not tolerate metformin (e.g., due to gastrointestinal symptoms) will continue to be followed for 12 months on an intent-to-treat basis. This is a minor risk and is reversible.

Adequacy of Protection against Risks

Recruitment and Informed Consent

The patients are volunteers that will be recruited through the primary care clinics. Potential subjects will then be screened in person to determine that they meet the initial recruitment criteria (such as age and BMI) and have no obvious contraindications to participating in the study. Screening of study participants will be conducted by a trained recruiter following a written manual of procedures. In a one-on-one, the potential participant(s) will be informed of the nature and requirements of the study, either via face-to-face interview or informed consent presentation. All patients will be given time to read the consent form and ask questions one-on-one with research staff. To continue, the participant must read and sign an informed consent to participate in further assessment and treatment.

Protection against Risks

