11.1.1.1 STUDY OVERVIEW

Brief Description of the Purpose of the Study – This is a pilot and feasibility study featuring a randomized controlled trial of an adapted telehealth-delivered Diabetes Prevention Program augmented by Community Health Workers plus/minus pharmacotherapy (metformin). The intervention and measurement protocols pose minimal risk to participants given our plans for the protection of research volunteers. We anticipate no major adverse events or serious adverse events except for nausea in some patients taking metformin. The data and safety monitoring plan for this trial focuses on close monitoring by the PIs and research staff in conjunction with a data safety and monitoring board (DSMB), along with prompt reporting of excessive adverse events and any serious adverse events to the NIH and to the IRB at UAB. The study procedures pose little to no risk for human subjects. However, a medical monitor (MM) will review the protocol and monitor conduct of this study.

Adherence Statement - The Data Safety Monitoring Plan (DSMP) outlined below will adhere to the protocol approved by the UAB IRB

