11.1.1.2 CONFIDENTIALITY

A. Protection of Subject Privacy – All volunteers are assured of their confidentiality both verbally and in the informed consent forms. The facilities are strictly limited to the staff of the research institution, clinics and to research volunteers. This is accomplished by a variety of stringent security measures. All medical records are stored in locked areas. Access to these areas is limited to the clinical support staff and the PI of the study. Volunteers' medical records are filed according to ID numbers. All forms on the chart, with the exception of consent form, display only the ID number.

B. Database Protection – Electronic data storage is similarly restricted with only the data management staff having access to databases containing confidential clinical records, i.e. those containing name or other identifying information.

C. Confidentiality during AE Reporting – Adverse events will be reported to the study PI, Project Manager, Medical Monitor, DSMB and Chair of the IRB throughout the trial. Adverse event data will be analyzed quarterly, but serious or life-threatening adverse events require immediate reporting and follow-up. AE reports and quarterly summaries will not include subject-identifiable material. Each will include the identification code only.

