11.1.1.3 ADVERSE EVENT INFORMATION

A. Definition - An adverse event (AE) is any untoward medical occurrence in a subject temporally associated with participation in the clinical study. An adverse finding can include a sign, symptom, abnormal assessment (laboratory test value, vital signs, electrocardiogram finding, etc.) or any combination of these. A Serious Adverse Event (SAE) is any adverse event that results in one or more of the following outcomes: death; a life-threatening event; inpatient hospitalization or prolongation of existing hospitalization; a persistent or significant disability/incapacity; a congenital anomaly or birth defect; important medical event based upon appropriate medical judgment.

B. Classification of AE Severity – AEs will be labeled according to severity which is based on their impact on the patient. An AE will be termed 'mild' if it does not have a major impact on the patient, 'moderate' if it causes the patient some minor inconvenience and 'severe' if it causes a substantial disruption to the patient's wellbeing. The Site Staff for this trial will be responsible for determining the 'severity' of AEs. Site Staff will also make an initial evaluation of the 'seriousness' of the AE in order to determine if the AE needs to be elevated to the MM immediately upon discovery. The MM will make the final and official determination of the 'seriousness' of an AE. We anticipate most adverse events will be "mild" and the participant will be able to resume daily activities within a day or two of reporting the event.

C. AE Attribution Scale – AEs will be categorized according to the likelihood that they are related to the study intervention. Specifically, they will be labeled as either related or unrelated to the study intervention, and this relationship will be confirmed by the Medical Monitoring Team (MMT) for this trial.

D. Expected Risks – This study does not involve major risk to screeners and trial participants. Efforts to minimize the potential risks of the assessment methods and outcome variables include frequent monitoring by the investigators to assure that no volunteer suffers any adverse effects from participating in the research. The expectedness of an AE will be determined by the Medical Monitoring Team (MMT).

The study procedures include:

- a) Body height and weight. There is minimal risk to participants from these measurements.

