- b) Finger stick blood sample. There is the possibility of pain and bruising on the finger where the finger prick is made. Aseptic (sterile) technique and trained personnel minimize these risks.
- c) Diet. Patients may modify their diet based on intervention recommendations that is safe for humans and has been tested repeatedly in clinical trials.
- d) Increased physical activity. Patients in the intervention arm will be counseled to increase physical activity to levels that are consistent with the recommendations for US adults (30 minutes of moderate intensity activity per day). There is the possibility of adverse events such as minor musculoskeletal problems, but risk is minimized by excluding potential participants with contraindications to exercise. Considering these types of events are expected in this trial they will not be recorded or reported unless they meet the definition of a Serious Adverse Event. Patients are counseled to secure physician approval before beginning any new exercise plan.
- e) Gastrointestinal (GI) upset from taking metformin. For patients enrolled in the lifestyle plus metformin recommendations, we will ask patients to monitor their symptoms. Metformin is recommended by the American Diabetes Association for the prevention of diabetes among those at high-risk. To minimize nausea and GI upset, in the Orientation for providers and provider handout on metformin therapy recommendations, materials will describe how to start patients at low dose of 250mg daily and increase to 250mg twice daily after 2 weeks as tolerated. Enrolled participants who do not tolerate metformin (e.g., due to gastrointestinal symptoms) will continue to be followed for 12 months on an intent-to-treat basis. This is a minor risk and is reversible.

E. SAE Reporting - SAEs that are unanticipated, serious, and possibly related to the study intervention will be reported to the Medical Monitoring Team and the UAB IRB in accordance with requirements. Anticipated SAEs or those unrelated to the study intervention will be reported to the same individuals/entities in accordance with requirements. Clinics will be required to report to the Medical Monitoring Team adverse events that are serious or in doubt about being serious within 24 hours of discovery. Other adverse events that are not serious but are unexpected and are associated with the study procedures will be reported within 10 days.

Data Quality and Safety Review Plan and Monitoring

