A1c	≥6.5%	At Visit or Within 1 week or sooner as indicated by exact value and judgment of Medical Monitor	Provide letter to PCP with A1c value and instruct the patient to notify their PCP within 1 week or sooner as indicated by exact value and judgment of Medical Monitor

D. Stopping Rules - This study will be stopped prior to its completion if: (1) adverse effects that significantly impact the risk-benefit ratio have been observed; (2) study recruitment or retention becomes futile; (3) any new information becomes available during the trial that necessitates stopping the trial; and (5) other situations occur that might warrant stopping the trial. Because one of the most likely reasons for stopping the trial is the inability to recruit the study sample, the PI will include an assessment of recruitment futility in the annual progress report to funder and will consult with a biostatistician if necessary to assess the impact of significant data loss due to problems in recruitment, retention or data collection.

E. Safety Review Plan - The PI will monitor the progress of the study weekly, including reasons for attrition and whether all participants met entry criteria. Further, progress and safety will be reviewed quarterly. These progress reports will include information on recruitment, retention/attrition, and AEs and will be provided to the Medical Monitor quarterly. The Medical Monitor will also receive a yearly report that details data relevant to the possible early termination of the study. We will establish a DSMB and we will provide reports to the DSMB prior to each meeting on adverse events and recruitment.

F. Informed Consent

Patients are volunteers that will be recruited through primary care clinics. The UAB's Institutional Review Board (IRB) as well as the IRBs of the partner institutions will approve the study protocol and all consent forms. Trained recruiters will obtain informed consent from all participants as well as HIPAA authorization. All questions and concerns are clarified before any forms are signed.

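### Only the metformin-recommendation arm is asked to monitor symptoms, so any by-arm view of non-serious gastrointestinal symptoms is open to ascertainment bias

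*Combined protocol and SAP*

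**What the plan says.** Under the GI-upset item of the risk list in Section 10.1, and in the same words under Expected Risks in Section 11.1.1.3, the plan states: "For patients enrolled in the lifestyle plus metformin recommendations, we will ask patients to monitor their symptoms". It describes no instrument, schedule or recording form for this, and makes no corresponding request of the lifestyle-only arm.

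The other routes by which events could come to light are not tied to an arm:

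- **Definition (Section 11.1.1.3, A):** "An adverse event (AE) is any untoward medical occurrence in a subject temporally associated with participation in the clinical study".
- **Change in Health History Questionnaire (Section 7), at 6 and 12 months:** "A self-report questionnaire captures changes in health outcomes that have occurred across the 6 months of the intervention". GI items are not mentioned.
- **Chart review (Section 7):** "For each of the participating patients in both arms, a retrospective chart review covering the period of the intervention will be done". The variables to be abstracted are not listed.
- **Reporting of non-serious events (Section 11.1.1.3, E):** "Other adverse events that are not serious but are unexpected and are associated with the study procedures will be reported within 10 days". GI upset is listed as an expected risk, and Section 11.1.1.1 says: "We anticipate no major adverse events or serious adverse events except for nausea in some patients taking metformin".

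On use of the data, Section 11.1.1.2 says "Adverse event data will be analyzed quarterly". Section 11.1.1.3 has each event labelled as related to the intervention or not, and its first stopping condition is that "adverse effects that significantly impact the risk-benefit ratio have been observed". Section 5 makes the trial open to patients, clinic staff, community health workers and the research staff who deliver the intervention.

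**The concern.** If one arm is told to watch for symptoms and the other is not, the first will tend to report more of them even when the true rates are equal. Knowledge of assignment can add to this, and participants in the metformin-recommendation arm also receive a metformin handout at baseline (Section 6.1.2). Prescribing is left to the provider (Section 2.2), so prompted reports may include people who never took the drug.

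What is at stake is the interpretation of GI reports. A reviewer who sees more of them in one arm at a quarterly review will want to know how many would have occurred under lifestyle change alone. That background figure is not collected in the same way. The same gap would carry into the planning of the larger trial of lifestyle plus metformin if pilot GI counts were used there.

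**Working it through.** The plan states no adverse-event rate or precision, so there is no figure to reproduce. The check has two parts.

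**1. Does another source collect GI symptoms equally in both arms?**

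| Source | Both arms? | Said to ask about GI symptoms? |
|---|---|---|
| Request to monitor symptoms (10.1 e; 11.1.1.3 D e) | No, metformin-recommendation arm only | Yes, by its place under GI upset |
| Adverse-event definition (11.1.1.3 A) | Yes | No method of elicitation given |
| Change in Health History Questionnaire (7) | Yes | No |
| Chart review (7) | Yes | No |
| 10-day reporting rule (11.1.1.3 E) | Yes | Covers unexpected non-serious events; GI upset is listed as expected |

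The only GI-specific step is the one-arm request. The plan also does not say whether expected, non-serious GI events are recorded at all. For minor musculoskeletal events it does say: they are left out unless serious.

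**2. What could unequal capture do?**

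Inputs from Section 12: 50 per arm (2 clinics × 25), or 40 after 20% attrition. Assumed, because the documents do not give them: a true GI rate *p* that is equal in both arms, and a lifestyle-only capture *s* relative to the other arm.

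- Spurious difference = *p* − *ps* = *p*(1 − *s*)
- Spurious ratio = *p* / (*ps*) = 1/*s*

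| *s* | Ratio | Difference, *p* = 5% | *p* = 10% | *p* = 20% |
|---|---|---|---|---|
| 0.75 | 1.33 | 1.3 points | 2.5 points | 5 points |
| 0.50 | 2.0 | 2.5 points | 5 points | 10 points |
| 0.25 | 4.0 | 3.8 points | 7.5 points | 15 points |
| 1.00 (equal capture) | 1.0 | 0 | 0 | 0 |

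In counts, with *p* = 20% and *s* = 0.5: 50 × 0.20 = 10 events against 50 × 0.10 = 5. No test is planned, but as a gauge, a two-sided 5% comparison of 20% with 10% (normal approximation, clustering ignored) would be nominally significant about 29% of the time with 50 per arm and 24% with 40.

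**Within-arm description.** This does not need the other arm. An observed 20% has a Wilson 95% interval of 11% to 33% with n = 50 (10 events), or 10% to 35% with n = 40 (8 events), again ignoring clustering.

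**The case against.** The strongest reply is that the sentence is a safety instruction for people who may be prescribed a drug, not a data-collection rule. Section 7 describes no GI diary or checklist in either arm. Section 13 plans by-arm summaries of completion, reasons for not completing and patient characteristics, and no adverse-event rates. Relatedness is decided event by event and confirmed by the Medical Monitoring Team. Neither the reporting of excessive events nor the stopping rule has an arm-based threshold, GI upset is called minor and reversible, and tolerability is not an endpoint.

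Much of this stands, and it rules out three stronger readings that a reader might infer:

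- **That GI symptoms are actively solicited in one arm.** The text says only that patients will be asked to monitor; collection is an inference.
- **That adverse-event rates by arm are biased in general.** The request sits under GI upset, the other sources are common to both arms, and serious events follow one rule.
- **That tolerability cannot be judged.** If events are recorded, a GI rate within the metformin-recommendation arm can be estimated, and participants who cannot tolerate the drug stay in follow-up for the full year.

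That diet change itself causes GI complaints is plausible but is not in the documents, and the point does not need it.

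The reply does not remove the narrower point. Events are still reviewed quarterly, judged for relatedness and weighed against benefit. Whoever does this for GI reports has prompted reports from one arm and no like-for-like background from the other.

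**Conclusion.** The point holds for non-serious GI symptoms viewed by arm. The direction of the possible bias is against the metformin-recommendation arm. What is weakened is the attribution of any excess to metformin over lifestyle change alone.

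The size cannot be derived from the documents. The ratio of 2 assumes equal true rates and half capture in the lifestyle-only arm; across the assumed range of capture (0.75 to 0.25) it runs from 1.33 to 4. If the request generates no recorded events, there is no bias, but there are then no GI data either, which is a reason to settle the recording rule first.

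This is a low-cost improvement to a pilot. It does not call the weight and HbA1c outcomes or serious-event reporting into question.

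**What to change.** 1. Add one short GI-symptom question, identically worded for both arms, to the Change in Health History Questionnaire at 6 and 12 months.
2. State whether expected, non-serious GI events are recorded, and apply the same rule in both arms.
3. Tabulate the answers by arm and by metformin use, and name metformin prescription among the chart-review variables so that use is known. Build the by-arm table from the common question and list reports arising from the monitoring request separately. The split by metformin use is descriptive, since use is not randomized.
4. Leave the existing safety request to participants in the metformin-recommendation arm in place.

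The cost is one item on a form already in use: 100 participants × 2 visits = at most 200 answers, plus more non-serious events recorded in the lifestyle-only arm. Sample size and visits do not change. Asking at every peer-coach call is not needed: at 22 calls (Section 3) to 26 (one before each session in Section 6.1.1), that would be 2,200 to 2,600 askings for 100 people, with review of positives on top.

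Two limits remain. Recall over about six months will miss some mild symptoms, though under the same procedure in both arms. Because assignment is known and the safety request stays, some difference in awareness may persist. The common question reduces the bias and may not remove all of it.
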